This is a single site, feasibility, randomized, dose-ranging clinical trial of remote ischemic preconditioning. During periods of active treatment, induced twice a day by using the autoRICTM device around both upper body extremities which would deliver four remote ischemic conditioning cycles of five minute intervals followed by five-minutes of normal blood flow. The RPreC intervention will be add-on therapy to guideline-based best standard medical prevention therapy. The study will have a randomized phase and a follow-up phase. 60 enrolled patients will be randomized 1:1:1 to 1 year of best standard medical care alone, best standard medical plus active once-daily RPreC, or best standard therapy plus active twice-daily RPreC. Following the 1 year randomized phase, the medical control group will cross over to once (10 patients) and twice (10 patients) daily RPreC for 1 additional year (staggered start design, allowing for collection of additional feasibility and safety data and control group adherence to follow-up). Primary outcome measures will be obtained at the end of the first randomized year.

C.2. Technology

Remote Ischemic Preconditioning Device: The autoRICTM device is a new, portable, automated conditioning device, designed and developed by CellAegis Devices Inc., Canada. The device consists of a Control Unit, Charging Cradle, a Power Adaptor, a Wall Mount for the charging cradle (with wall plug and screws) and Applicator Cuffs. The control unit is a stand-alone reusable controller that controls the inflation and deflation cycles of the Applicator Cuff. The Control Unit clicks into the disposable Applicator Cuff when it is ready for use. The Applicator Cuff is a single-used, disposable cuff that is fastened using Velcro into which a 'one button' battery-driven actuator system inserts. This provides for a mobile 'point-of-care' delivery of RIC that will not impose on other care delivery, and requires no special expertise for its use. The active device is programmed to inflate the cuff to 200 mmHg for five (5) minutes (ischemia) then be deflated for five (5) minutes (reperfusion) completing one cycle of ischemia-reperfusion; the RIC therapy cycle consists of a total of four (4) cycles of ischemia-reperfusion, which the autoRIC Device is programmed to automatically deliver.

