All participating investigators and site personnel that will be performing the autoRIC procedure will be trained in the use of the study device prior to participating in the study. Device training will be conducted by the Principal Investigator. Training will be done according to the autoRIC User Manual and will include instructions on charging the device prior to the first use, recharging the device after each procedure, verifying the device is charged prior to each procedure, recognizing and addressing the different Warning/Error indications (e.g., battery light flashing blue, indicating that the battery is low but can still perform at least one procedure, battery light steady red, indicating battery low error – not enough battery power to run a complete procedure, etc.) and specific instructions for returning the device to the sponsor in the event of an error notification that cannot be addressed by the site personnel, or a failure of the device to charge after three hours.

All device training will be documented in a training log that will be maintained in the site regulatory binder.

C.3. Subjects

60 subjects will be identified prior to discharge from the inpatient Stroke Service, which manages over 350 patients yearly, and from the inpatient rehabilitation unit that cares for 100 patients yearly with disabling stroke. They will also be identified in our outpatient stroke clinic that manages over 500 patients yearly. Based upon a review of the past 5 years of stroke patients evaluated, we anticipate that at least 20% are likely to be eligible. Potential participants will be approached by an investigator and given the informed consent from to review. Enrolled subjects will be randomized 2:1 to active treatment (40 patients) and control (20 patients).

C.3.1.Entry Criteria

To enter the study screening phase, patients must meet all of the following inclusion and exclusion criteria:

Inclusion Criteria

I. Clinical

- 1. Clinical lacunar stroke syndrome within the past 6 months (from among the following 12 syndromes as per SPS3 criteria: pure motor hemiparesis (PMH), pure sensory stroke, sensorimotor stroke, ataxic hemiparesis, dysarthria-clumsy hand syndrome, hemiballism, PMH with facial sparing, PMH with horizontal gaze palsy, PMH with contralateral III palsy, PMH with contralateral VI palsy, cerebellar ataxia with contralateral III palsy, pure dysarthria)
- 2. Absence of signs or symptoms of cortical dysfunction

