- 3. No proximal large vessel atherosclerosis, intracranial atherosclerosis or cerebellar stroke.
- 4. No major cardioembolic source requiring anticoagulation or other specific therapy

II. Imaging

- 1. MRI presence of a small subcortical ischemic per SPS criteria, any 1 or more of:
 - a. Diffusion-weighted imaging lesion < 2.0cm in size at largest dimension and corresponding to the clinical syndrome.
 - b. Well delineated focal hyperintensity <2.0 cm in size at largest dimension (including rostro-caudal extent) on FLAIR or T2 and clearly corresponding to the clinical syndrome. If other focal hyperintensities are present, the case will be discussed with the PI prior to randomization
 - c. Multiple (at least 2) hypointense lesions of size 0.3-1.5 cm at largest dimension (including rostro-caudal extent) only in the cerebral hemispheres on FLAIR or T1 in patients whose qualifying event is clinically hemispheric
 - d. Well delinated hypointense lesion <1.5 cm in size at the largest dimension (including rostro-caudal extent) on FLAIR or T1 corresponding to the clinical syndrome. MRI must be done at least 1 months after the qualifying stroke
- 2. Absence of cortical stroke and large (> 1.5cm) subcortical stroke, recent or remote
- 3. White matter hyperintensity score of 2 (moderate) or 3 (severe) on the European Scale of Age-Related White Matter Change
- 4. No evidence of cerebral amyloid angiopathy as per Boston Criteria.

Exclusion Criteria

To be eligible for entry into the study, none of the following criteria may be present:

- 1. Disabling stroke (Rankin Scale \geq 4)
- 2. Previous intracranial hemorrhage (excluding traumatic) or hemorrhagic stroke
- 3. Age under 40 years
- 4. High risk of bleeding (e.g. recurrent GI or GU bleeding, active peptic ulcer disease, etc.)
- 5. Anticipated requirement for long term use of anticoagulants (e.g. recurrent DVT)
- 6. Prior cortical or retinal stroke (diagnosed either clinically or by neuroimaging), or other prior cortical or retinal TIA
- 7. Prior ipsilateral carotid endarterectomy
- 8. Impaired renal function: estimated GFR <40

- 9. Patients treated with hemodialysis
- 10. Intolerance or contraindications to aspirin or clopidogrel (including thrombocytopenia, prolonged INR)
- 11. Mini Mental Status Exam score < 24 (adjusted for age and education)
- 12. Medical contraindication to MRI
- 13. Pregnancy or women of child-bearing age who are not following an effective method of contraception

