To ensure that appropriate ethical consideration is given to the welfare of the patients enrolled in the study, a Data and Safety Monitoring Board (DSMB) will oversee the trial. The DSMB will review the incidences and circumstances of adverse events that occur during the course of the trial. Formal interim analysis will occur at the half way -point, after enrolled patients have completed 50% of patient months of follow up. If the incidence of recurrent stroke or all serious adverse events is higher in the combined device arm than the control arm the study will be placed on hold. The DSMB will conduct a detailed analysis of the safety data. The DSMB may recommend making changes it deems necessary in the interests of the safety or well-being of the study subjects, or suspending or stopping the study. Final determination of a formal stopping rule will be the prerogative of the appointed DSMB.

The members of the DSMB are:

[name], Stroke Neurologist, University of Southern California [name], Stroke Neurologist, Rancho Los Amigos National Rehabilitation Center

C. 14.2. Statistical Design and Analysis Plan

The demographic and baseline clinical characteristics of the study population will be delineated with standard descriptive statistics. Categorical variables describing the clinical history, examination findings, and initial treatment will be summarized by frequencies. Continuous variables such as vital signs, laboratory results, and time variables that follow normal distribution

will be characterized by means, standard deviations, and 95% confidence intervals (CI). Ordinal and non-normally distributed variables (such as the NIHSS) will be characterized by medians and interquartile ranges. RIPC and control patients will be compared to delineate covariate balance. Wilcoxon Rank-Sum tests will be used for continuous or ordinal variables; Fisher's exact tests and chi-square tests will be used for grouped or nominal categorical variables. Comparisons of changes across time (i.e. base to one year) within and between groups will be made using repeated measure analysis variance methods or the non-parametric analog.

C. 14.3. Selection and Analysis of Endpoints

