Feasibility: Because the primary aim of this trial is assessing feasibility and tolerability, the primary endpoints are descriptive statistics describing the implementation of the RPreC procedure, including behavioral adherence to treatment, physiologic attainment of limb ischemia, and patient self-reported comfort-discomfort during treatment. The simplicity of these endpoints reduces the likelihood of problems in the analysis and interpretation of these endpoints. The procedure will be considered adequately feasible if adherence and physiologic targets are attained in 75% or more of cases. At this early stage of development, observations and lessons from individual cases may warrant procedural protocol changes to optimize the intervention. Such flexible, developmental iterations of the intervention will be closely discussed with, and supervised by, the study DSMB.

Safety: The lead safety endpoint will be all serious adverse events. Secondary safety endpoints will be deep and superficial vein thrombosis and all cause mortality.

Efficacy: The lead efficacy endpoint will be volumetric progression of white matter ischemic injury on magnetic resonance imaging (biomarker efficacy). The primary MRI endpoint will be the proportion of patients with increase in total white matter hyperintensity volume (as percent of total brain volume) above 1.0%. (This value represents the threshold for the upper quintile of progression in the SCOPE trial. Proportion of patients with progression in the upper quintile was the most sensitive MR endpoint analyzed in the SCOPE substudy.) Additional MRI endpoints analyzed will include mean progression total white matter hyperintensity, mean and quintile progression in deep white matter hyperintensity, progression in total brain atrophy, and progression in DTI anisotropy. The MR imaging measures of white matter injury progression, ascertained by automated analysis and blinded readers, are not subject to bias.

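### The additional and exploratory continuous outcomes are compared as raw change from baseline, with no baseline adjustment; with equal SDs this loses (1 − ρ)/2 of the information

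*Combined protocol and SAP*

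**What the plan says.** C.14.2 gives one sentence for all outcomes of this kind. Its subject is "Comparisons of changes across time (i.e. base to one year) within and between groups", and the method it states is that these comparisons "will be made using repeated measure analysis variance methods or the non-parametric analog". It names no term to be tested, no rank procedure, no rule for choosing that procedure and no covariate. The same section says that "RIPC and control patients will be compared to delineate covariate balance", but nothing follows from that comparison.

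C.14.3 lists the outcomes to which the sentence would apply. After the lead MRI endpoint come "mean progression total white matter hyperintensity", deep white matter hyperintensity, brain atrophy and DTI anisotropy as additional MRI endpoints. Gait and cognitive z scores follow as explored endpoints. The lead MRI endpoint is of another kind: "The primary MRI endpoint will be the proportion of patients with increase in total white matter hyperintensity volume (as percent of total brain volume) above" a cut-off, which is set at 1.0%.

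On group sizes, C.3 says "Enrolled subjects will be randomized 2:1 to active treatment (40 patients) and control (20 patients", and C.1 says "60 enrolled patients will be randomized 1:1:1 to 1 year of best standard medical care alone" with two device arms beside it. Both pool to 40 device v 20 control.

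**The concern.** In a randomised comparison of a continuous outcome measured at baseline and at one year, the usual choice is to compare the one-year values adjusted for baseline. Subtracting the baseline instead fixes the regression slope at 1. Where the true slope is below 1, the subtraction over-corrects, and part of any chance baseline difference between arms stays in the estimate with its sign reversed.

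At stake is the precision of the continuous results under Aim 3, which looks for signals of efficacy. With 20 controls those estimates will be imprecise in any case, and the baseline value that would sharpen them is already part of the plan for MRI and cognition. The unnamed rank alternative also leaves the choice of test open until the data are seen.

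**Working it through.** **The plan's own figures.** The documents state no SD, effect size, correlation or power for any between-group comparison of change, so there is no figure on this point to reproduce. The only power figures, in C.14.4, are for adherence. They reproduce with an exact one-sided binomial test to within 0.001. For N = 40, true adherence 90% and alpha 0.05, the test rejects at 35 or more adherent patients (size 0.043), with power 0.794 as stated. Nothing below affects them.

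**Inputs.** The method and the two time points come from C.14.2; 40 v 20 comes from C.3 (and C.1 when pooled). The correlation ρ and equal SDs are assumptions.

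**Step 1: variances.** Set the SD to 1 at both times. With two time points, the group-by-time test in repeated-measures ANOVA is the t-test on change.

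- Change score, variance per patient: 2(1 − ρ)
- ANCOVA, residual variance per patient: 1 − ρ²
- Ratio: (1 − ρ²) / [2(1 − ρ)] = (1 + ρ)/2
- Information lost: 1 − (1 + ρ)/2 = (1 − ρ)/2

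The group sizes cancel, so the percentage does not depend on 40 v 20.

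**Step 2: cost of estimating the slope.** At N = 60 this multiplies the ANCOVA variance by about 57/56 = 1.018.

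| ρ (assumed) | Change | ANCOVA | Loss | Loss net of slope cost |
|---|---|---|---|---|
| 0.3 | 1.40 | 0.91 | 35% | 34% |
| 0.5 | 1.00 | 0.75 | 25% | 24% |
| 0.7 | 0.60 | 0.51 | 15% | 13% |
| 0.9 | 0.20 | 0.19 | 5% | 3% |
| 0.95 | 0.10 | 0.0975 | 2.5% | 0.8% |
| 0.98 | 0.04 | 0.0396 | 1% | −0.8% (no gain) |

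Simulation of 40,000 trials at 40 v 20 gave losses of 23.7%, 13.2%, 3.6% and 0.7% at ρ = 0.5, 0.7, 0.9 and 0.95, in line with the last column. In patient terms, 60 analysed by ANCOVA are worth 60/0.75 = 80 analysed by change score at ρ = 0.5, and 60/0.95 = 63 at ρ = 0.9, before the slope cost.

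**Step 3: unequal SDs.** If the 12-month SD is k times the baseline SD, the variances are k² + 1 − 2ρk for change and k²(1 − ρ²) for ANCOVA. They differ by (1 − ρk)², which is never negative. With k = 1.1 the loss is 18% at ρ = 0.5 and 8% at ρ = 0.7. With k = 1.2 and ρ = 0.95 it is 12%. Unequal SDs can therefore move the loss either way.

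**Step 4: baseline imbalance.** The standard error of the baseline difference is √(1/40 + 1/20) = 0.27 SD. A difference of that size shifts the change-score estimate by (1 − ρ) × 0.27 SD: 0.14 SD at ρ = 0.5, 0.08 at 0.7, 0.03 at 0.9 and 0.01 at 0.95. The ANCOVA estimate does not move with it.

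This is the loss in Step 1 seen from another side. With equal SDs, 2(1 − ρ) − (1 − ρ²) = (1 − ρ)², which is exactly the variance that the shift contributes. At ρ = 0.5, 1.00 − 0.75 = 0.25 = 0.5². The two must not be added.

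**The case against.** The strongest case against is that the loss may be small and falls on outcomes of low rank. White matter and brain volumes measured twice on one scanner could plausibly have a high ρ (an assumption), and with equal SDs the loss is then a few percent or nothing. C.14.4 calls the study a pilot for efficacy and does not claim adequate power. Over repeated randomisations the change-score estimate is unbiased, and its confidence interval already allows for chance imbalance. All of this stands. It limits the size of the point, but it is not a reason to leave out a covariate that the trial already plans to collect.

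Four stronger readings are tempting, and the documents do not support them.

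- A reader might infer a fixed loss of 15–25%. That needs ρ between 0.5 and 0.7 and equal SDs, and the documents give neither.
- A reader might infer that the group main effect will be tested, which would average in the baseline and halve any treatment effect. The sentence speaks of comparing changes across time between groups, which is the group-by-time contrast.
- A reader might take the rank analog to be the Friedman test, which does not compare arms. The plan names no test, so the fault is that it is unnamed.
- A reader might infer that the trial's main results, or the variances for a successor trial, are at risk. C.11 says that the primary endpoint makes no use of the control arm, the lead MRI endpoint is a proportion, and C.14.4 ties planning of the successor to adherence.

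**Conclusion.** The point holds for the additional and exploratory continuous outcomes only. For these, C.14.2 is the sole stated method, and no section adjusts for the baseline value. With two time points and equal SDs the loss against ANCOVA is (1 − ρ)/2: from 35% at ρ = 0.3 to 5% at 0.9, and about nil at 0.98 after the slope cost. Chance baseline imbalance, with a standard error of 0.27 SD for pooled device v control, is how that loss shows itself in a single trial. It is not a second harm.

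The formula does not cover a rank analysis or a repeated-measures analysis that uses all visits. The adherence endpoint and the binary MRI endpoint are unaffected. This is an improvement at almost no cost to secondary estimates in a pilot, and no threat to the trial's main conclusions.

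**What to change.** Keep the within-group part of the sentence in C.14.2 and replace the between-group part with:

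> Each 12-month continuous outcome is compared between randomised arms by ANCOVA with its baseline value as covariate, reported as the adjusted difference with 95% CI. Where the distribution is markedly non-normal, rank ANCOVA (ranked 12-month value adjusted for ranked baseline) is used. For cognition, measured at Months 1, 3, 6, 9 and 12, a mixed model with the post-baseline visits as outcomes and baseline as covariate gives the 12-month contrast.

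Apply the same to gait once its schedule is reconciled. Section A.3 has gait measured at baseline, but the C.10.1 baseline list has no accelerometer. The visit lists in C.10.2 to C.10.4 first show it at Month 3. Any analysis of change in gait, planned or proposed, needs the baseline value.

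The cost is wording in the analysis plan and one degree of freedom per ANCOVA. The mixed model also estimates covariance parameters: 5 × 6/2 = 15 if unstructured over the five cognition visits. With 20 controls the plan should therefore name a simpler structure to fall back on. No new data are needed for MRI or cognition. A log transform of volumes and the entry white matter grade as a further covariate are not needed for this fix. The first would change the scale of the effect, and no benefit has been shown for the second.

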During periods of active treatment, RPreC will be induced twice a day by using the autoRIC[™] device (which delivers four remote ischemic conditioning cycles of five minute intervals followed by five-minutes of normal blood flow) around both upper body extremities. The RPreC intervention will be add-on therapy to guideline-based best standard medical prevention therapy. The study will have a randomized phase and a follow-up phase. 60 enrolled patients will be randomized 2:1 to best standard medical care plus active RPreC for 1 year and then follow-up for 1 year versus best standard medical care alone for 1 year and then active RPreC for 1 year. Primary outcome measures will be obtained at the end of the first randomized year (staggered start RCT design). Successful completion of this trial will delineate the feasibility and safety, and explore biomarker indicators of potential efficacy, of inducing brain ischemic tolerance in small vessel stroke-prone patients.

A.1. Specific Aim 1: Feasibility

To establish the feasibility of remote ischemic preconditioning as a sustained therapy for prevention of ischemic brain injury from cerebral small vessel disease.

This aim will be accomplished by demonstrating the remote ischemic preconditioning treatment can be successfully implemented with more than 75% adherence among enrolled patients throughout the 1-year of active treatment. Both patient self-report and remote physiologic monitoring will be performed to quantify patient behavioral adherence to the treatment regimen, and remote physiologic monitoring will be used to quantify physiologic attainment of brief ischemia states in the upper extremities. Establishment of feasibility will allow for subsequent larger, definitive clinical trials of RPreC as a treatment to confer long-term protection against ischemic brain injury due to cerebral small vessel disease.

A.2. Specific Aim 2: Safety

To determine the safety of remote ischemic preconditioning as a sustained therapy for prevention of ischemic brain injury from cerebral small vessel disease.

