Additional efficacy endpoints explored will include accelerometer assessment of gait quantity and quality in real-world activity; z scores on individual tests and summed performance on the cognitive battery, and incident ischemic stroke, transient ischemic attack, hemorrhagic stroke, myocardial infarction, and cardiovascular death. To protect against bias in ascertainment of the recurrent stroke secondary endpoint, analysis to include a) adjudication of potential endpoint stroke events by 2 independent blinded neurologists (preventing rater bias), and b) administration of the Questionnaire to Verify Stroke Free Status at each follow-up visit, to trigger endpoint evaluations (preventing ascertainment bias).

C.14.4. Sample Size Calculations

Subject size is typical sample size for a feasibility study with a device. We are looking at adherence in order to plan a larger phase II/III successor trial.

Sample Size Justification

The primary feasibility and study endpoint is RPreC adherence at 12 months. As we do not expect clinically important differences in adherence among the three groups, it may be possible to combine two or all three groups. In this study, we also wish to test the null hypothesis that the true adherence is at least 75%. The table below gives the lower 90% or 95% confidence bound for 90%, 95% or 100% observed adherence as a function of sample size and the corresponding statistical power for testing the null hypothesis that the true population adherence is 75% versus the one sided alternative of greater than 75%. The current study is not necessarily sufficiently powered for any of the safety or efficacy outcomes. Therefore this is a pilot study in terms of safety and efficacy.

Lower 90% or 95% one sided confidence bound for true adherence

| | adherence=90% | | adherence=95% | | adherence=100% | |
|----|---------------|------------|---------------|------------|----------------|----------------|
| | 90% | 95% | 90% | 95% | | |
| Ν | confidence | confidence | confidence | confidence | 90% confidence | 95% confidence |
| 20 | 75.5% | 71.8% | 81.9% | 78.5% | 89.1% | 86.1% |
| 40 | 81.0% | 78.5% | 87.2% | 85.1% | 94.4% | 92.8% |
| 60 | 83.1% | 81.2% | 89.2% | 87.6% | 96.2% | 95.1% |

Power for one sided test against null hypothesis of 75% vs > 75%

| | adherence=90% | | adherence=95% | | adherence=100% | |
|----|---------------|------------|---------------|------------|----------------|------------|

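### C.14.4 states the adherence null backwards in one sentence, A.1 and C.14.3 disagree at exactly 75%, and the tabulated power does not describe the C.14.3 feasibility benchmark

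*Combined protocol and SAP*

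**What the plan says.** Three places set a 75% criterion for adherence.

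- **A.1 (Specific Aim 1)** counts the feasibility aim as met if treatment is delivered "with more than 75% adherence among enrolled patients throughout the 1-year of active treatment". This is a strict inequality.
- **C.14.3 (Feasibility)** says "the primary endpoints are descriptive statistics describing the implementation of the RPreC procedure" and then gives the benchmark: "The procedure will be considered adequately feasible if adherence and physiologic targets are attained in 75% or more of cases". This is inclusive, and has no test, alpha or confidence bound attached.
- **C.14.4 (Sample Size Justification)** adds a test: "In this study, we also wish to test the null hypothesis that the true adherence is at least 75" per cent. The next sentence describes the tables as giving power for "testing the null hypothesis that the true population adherence is 75% versus the one sided alternative of greater than 75" per cent, and the power table is headed "Power for one sided test against null hypothesis of 75% vs > 75" per cent. Powers are given at alpha 0.10 and 0.05 for N = 20, 40 and 60, and neither alpha is chosen.

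On the number analysed, C.3 puts 40 of the 60 patients on active treatment, and C.11 says the primary endpoint makes no use of the control group. C.14.4 nevertheless allows that "it may be possible to combine two or all three groups". The purpose is stated there too: "We are looking at adherence in order to plan a larger phase II/III successor trial".

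**The concern.** Two adjacent sentences in C.14.4 put the null on opposite sides of 75%. If the null is that adherence is at least 75%, then failing to reject it could be read as support for adequate adherence, and a small study with a poor result can fail to reject. A.1 and C.14.3 also use different inequalities, so one attainable result is feasible under one section and not under the other.

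The third issue concerns interpretation. The benchmark looks only at the observed proportion, whereas the test asks whether 75% can be excluded. The plan does not say how the two relate. The adherence result is meant to inform a successor trial, so whoever plans that trial needs to know whether a finding of feasibility carries the error control shown in the tables. It does not.

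**Working it through.** **Inputs.** The threshold is 75% (A.1, C.14.3, C.14.4). Alpha is 0.10 or 0.05 and N is 20, 40 or 60 (C.14.4 tables). There are 40 device patients (C.3). Assumptions: adherence is a yes/no per patient, all 40 are analysed, and adherence is taken alone unless stated. X is the number adherent, binomial(N, p).

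**1. Reproducing the power table.** The exact one-sided test of 75% versus more than 75% rejects at the smallest k with P(X ≥ k | 0.75) ≤ alpha. For N=40, P(X ≥ 33) = 0.182, P(X ≥ 34) = 0.0962 and P(X ≥ 35) = 0.0433. The test therefore needs 34/40 (85.0%) at alpha 0.10 and 35/40 (87.5%) at alpha 0.05.

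| True adherence | alpha | Computed power | Plan |
|---|---|---|---|
| 90% | 0.10 | P(X ≥ 34) = 0.9005 | 0.901 |
| 90% | 0.05 | P(X ≥ 35) = 0.7937 | 0.794 |
| 95% | 0.10 | P(X ≥ 34) = 0.9966 | 0.997 |
| 95% | 0.05 | P(X ≥ 35) = 0.9861 | 0.986 |

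All 12 numeric cells for 90% and 95% agree to within 0.001. The tabulated lower bounds agree with exact (Clopper-Pearson) bounds to about 0.1 percentage point. So the table uses a null at 75% and an alternative above it.

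**2. The reversed null taken literally.** Evidence against a null of at least 75% is a low count. For N=40, P(X ≤ 24 | 0.75) = 0.0262 and P(X ≤ 25 | 0.75) = 0.0544, so alpha 0.05 rejects only at 24 or fewer. A result of 25/40 (62.5%) does not reject. The probability of not rejecting, P(X ≥ 25 | p), is 0.44, 0.69 and 0.88 at a true 60%, 65% and 70%.

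**3. The two inequalities.** 0.75 × 40 = 30. C.14.3 passes at 30/40, while A.1 needs 31/40. P(X = 30) is 0.11, 0.14 and 0.11 at a true 70%, 75% and 80%. Exactly 75% can be observed only when N is a multiple of 4: it can at 20, 40 and 60, but not at 37, 38 or 39 (0.75N = 27.75, 28.5, 29.25).

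**4. The benchmark beside the test.** On adherence alone, C.14.3 passes with probability P(X ≥ 0.75N | p):

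| N | Passes at | True 65% | True 70% |
|---|---|---|---|
| 20 | 15 | 0.25 | 0.42 |
| 40 | 30 | 0.12 | 0.31 |
| 60 | 45 | 0.07 | 0.24 |

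At 30/40 the one-sided exact 95% lower bound is the 0.05 quantile of Beta(30, 11), which is 61.3%. At the test's cut-offs the bounds just clear 75%: 75.15% at 34/40 (90% confidence) and 75.5% at 35/40 (95% confidence).

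**5. The physiologic target.** C.14.3 requires this as well, so the values in step 4 are upper limits. As an illustration, suppose each case must meet both targets independently, with physiologic attainment of 95% or 90% (assumed). At a true adherence of 70% the joint rate is 0.70 × 0.95 = 0.665 or 0.70 × 0.90 = 0.63, and P(X ≥ 30 | 40) falls from 0.31 to 0.17 or 0.08.

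**The case against.** The strongest reply is that the plan already keeps the benchmark and the test apart. The power table is correctly headed, C.14.4 introduces the test as an addition, and C.14.3 calls the endpoints descriptive. A descriptive benchmark with a test alongside is a normal feasibility design. This stands. A reader might infer that the plan claims the tabulated power for the C.14.3 decision, or that the sample size justification is therefore wrong. The documents support neither: no sentence attributes that power to the benchmark, and the table is right for the test it names. Nor is C.14.3 the only stated criterion, since A.1 gives one too.

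A reader might also count every result that passes the benchmark but does not reject in the test as an error. At true adherence of 80% to 95% that is not so. A verdict of feasible is then correct by the plan's own target, and the gap reflects the test's limited power near 75%. Only declarations at true values below 75% are wrong.

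The reversed null is very probably a slip, because the next sentence, the heading and the tabulated powers settle the direction. The clash of inequalities matters at a single result, which dropout could make unattainable. Both points limit the consequence, but the text still needs correcting.

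**Conclusion.** Wrong as written, and minor. One C.14.4 sentence states the null in the wrong direction. A.1 and C.14.3 give opposite verdicts at exactly 75%. These two findings need no assumption beyond the text, although the sizes attached to them assume N=40 and a per-patient yes/no.

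The tabulated alpha and power belong to the C.14.4 test and do not carry over to the C.14.3 benchmark. With N=40, the benchmark could wrongly declare feasibility with probability up to 0.12 at a true 65% and up to 0.31 at a true 70%. These depend on reading a case as a patient, which the plan does not define. If adherence is instead a mean percentage of cycles, the binomial figures do not apply to C.14.3, but the tabulated power still describes only the test. Nothing here shows that the sample size or the tables are in error.

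**What to change.** 1. In C.14.4, restate the null as true adherence of 75% or less, tested one-sided against adherence above 75%.
2. Use the same inequality in A.1 and C.14.3.
3. In C.14.3, report observed adherence with its one-sided exact lower confidence bound beside the feasibility verdict. State that the tabulated alpha and power refer to the C.14.4 test and not to the benchmark.

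Whether the benchmark or the test governs, which patients form the analysis N and which alpha applies are for the sponsor to decide and record. Raising the bar to the test's cut-off is not required.

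The cost is one sentence each in A.1 and C.14.4 and a short addition to C.14.3. The bound is of a type C.14.4 already tabulates. Sample size, feasibility bar, tables and data collection do not change.
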